**Effects of acupressure on psychological distress,
depression among nurses in a medical center: a single-
blind randomized controlled trial**

NCT Number: NCT06946888

Date: December 31, 2024

Study Title

Effects of Acupressure on Psychological Distress and Depression Among Nurses in a Medical Center: A Single-Blind Randomized Controlled Trial

NCT Number: NCT06946888

Date: May 21, 2024-December 31, 2024

Background

Clinical nurses are routinely exposed to occupational stressors such as shift rotations, emotional labor, and high patient acuity, placing them at elevated risk of psychological distress and burnout (Zeiher et al., 2022; Katsiroumpa et al., 2025). Compared with other healthcare professionals, nurses report higher rates of emotional exhaustion and post-traumatic stress symptoms, particularly in the aftermath of the COVID-19 pandemic.

[figure not shown]
Acupressure is a complementary therapy that involves applying manual pressure to specific acupoints along the body's meridians to promote physiological and emotional regulation. Among the most studied acupoints for psychological symptoms are Shenmen (HT7) and Neiguan (PC6). HT7 is traditionally used to calm the spirit and regulate mood, and is commonly applied in treating insomnia and anxiety (Lee et al., 2019; WHO, 2008). PC6 is associated with regulating heart rhythm, relieving palpitations, and reducing stress (WHO, 2008; Lee et al., 2023). Prior studies have demonstrated that stimulation at HT7 and PC6 can reduce anxiety and depressive symptoms in patients recovering from COVID-19 (Liang et al., 2024) and improve mood stability in cardiac populations (Bal & Gun, 2024). Systematic reviews further confirm the potential of these acupoints in alleviating depression and anxiety (Lin et al., 2022).

Despite this evidence, research applying acupressure as a self-care intervention for healthcare workers—especially nurses—remains scarce. Given the high psychological demands of nursing work, evaluating accessible, low-cost interventions that nurses can self-administer without disrupting workflow is critically important. This trial addresses that gap by assessing the effects of self-administered acupressure on depressive symptoms, psychological distress, emotional distress, anxiety, job stress, occupational burnout, and resilience in clinical nurses.

Objective

This study aimed to examine the effects of self-administered acupressure at the Shenmen (HT7) and Neiguan (PC6) points on emotional distress, anxiety, depression, stress, work-related fatigue, and resilience among clinical nurses.

Methods

This study adopted a single-blind randomized controlled trial (RCT) design. It was approved by the Institutional Review Board of a medical center (IRB No. 24-CT6-13) and registered at ClinicalTrials.gov (NCT06946888). The study was conducted from June 13, 2024, to September 22, 2024. Participants included nurses aged 20 and above working in clinical departments. Exclusion criteria included: (1) refusal or inability to comply with the study; (2) non-clinical roles (e.g., administrative units, supply departments); and (3) pregnancy. Out of 463 screened nurses, 160 were eligible based on the Brief Symptom Rating Scale (BSRS-5 ≥ 4) or Distress Thermometer score ≥ 3 and agreed to participate. They were randomly assigned via computer to the intervention group (n=80) or control group (n=80).

Interventions

Participants in the intervention group received in-person instruction from a trained research assistant on how to self-administer acupressure targeting two specific acupoints on each hand—Shenmen (HT7) and Neiguan (PC6)—**resulting in a total of four acupoints (two on each hand)**. Participants were guided to apply approximately 3 kg of thumb pressure to each acupoint until a sensation of soreness or tingling was perceived. Each acupoint was stimulated with 15 rhythmic presses (approximately 30 seconds per point), totaling about 2 minutes per session for all four acupoints. The intervention was performed **twice daily for two consecutive weeks**, and participants were provided with illustrated instructions (Figure 1) and a daily acupressure log to record adherence. The **control group** received no intervention. **Although the intervention lasted 2 weeks, all participants in both groups were followed for 8 weeks and completed weekly questionnaires throughout the follow-up period.**

[figure not shown]

Figure 1. Anatomical locations of Shenmen (HT7) and Neiguan (PC6) acupoints.

HT7 (Shenmen) is located at the wrist crease on the radial side of the flexor carpi ulnaris tendon.

PC6 (Neiguan) is found approximately two cun (about three finger-widths) proximal to the wrist crease, between the palmaris longus and flexor carpi radialis tendons.

Instruments

Data were collected using self-administered questionnaires, which included measures of emotional distress, distress thermometer, Taiwanese Depression Scale, State Anxiety

Inventory, Nurse Stress Checklist, Occupational Fatigue Inventory, Resilience Scale, and basic demographic information. All instruments were used with permission from the original authors.

(1) Demographic Data:

Information collected included age, date of birth, gender, education level, current academic enrollment, marital status, number of children, living arrangements, religious beliefs, medical history, medication use, hospitalization experience, physical activity, stress-relief methods, work unit and department, experience with COVID-19 patient care, employment start date, external hospital experience, total years in nursing, self-reported sleep quality (1–10), and presence of sleep disorders.

(2) Emotional distress:

Emotional distress was measured using the Distress Thermometer (DT), a single-item self-report screening tool rated from 0 (no distress) to 10 (extreme distress). Higher scores indicate greater emotional distress, and participants were asked to report their overall distress during the past week, including the current day. The DT has demonstrated adequate psychometric properties across validation studies, with sensitivity ranging from 0.50 to 1.00 (median = 0.83) and specificity ranging from 0.36 to 0.98 (median = 0.68) (Donovan et al., 2014).

For the purpose of this study, a **DT cut-off score of ≥ 3** was adopted as an inclusion criterion. This threshold has been recommended in a large-scale validation study as an efficient marker of clinically elevated distress (Cutillo et al., 2017). Other studies have shown that optimal DT cut-offs vary across settings, typically ranging from 3 to 5 (Donovan et al., 2014), while clinical practice often applies a threshold of ≥ 4 or ≥ 5 (Ownby, 2019). Using ≥ 3 in this study was intended to maximize sensitivity and minimize the risk of under-identification in a nursing population considered at high risk for psychological distress.

(3) Psychological distress:

Psychological distress was measured using the 5-item Brief Symptom Rating Scale (BSRS-5; Lee et al., 2010), a validated screening tool for general psychological distress. The BSRS-5 assesses the subjective severity of (1) anxiety (feeling tense or keyed up), (2) depression (feeling blue), (3) hostility (feeling easily annoyed or irritated), (4) inferiority (feeling inferior to others), and (5) insomnia (difficulty falling asleep). Each item is rated on a 5-point Likert scale ranging from 0 (“not at all”) to 4 (“extremely severe”), with

higher scores indicating greater psychological distress. Total scores range from 0 to 20, and the BSRS-5 demonstrated good internal consistency in the present study (Cronbach's $\alpha = .86$).

Validation studies have suggested that total scores of 3–4 represent an optimal threshold for identifying clinically relevant distress, based on receiver operating characteristic (ROC) curve analysis (Lee et al., 2010). At these cut-offs, the BSRS-5 showed high accuracy (AUC = 0.92), with good sensitivity (0.83) and specificity (0.86). Based on this evidence, the present study adopted a **BSRS-5 total score of ≥ 4** as one of the inclusion criteria, ensuring that participants with at least mild psychological distress were captured.

(4) Depressive symptoms:

Depressive symptoms were assessed using the Taiwanese Depression Scale (TDS; Lee et al., 2000), which has demonstrated strong psychometric properties in Taiwanese populations. The TDS consists of 18 items rated on a 4-point Likert scale: 0 = none or seldom (less than one day per week), 1 = sometimes (one to two days per week), 2 = often (three to four days per week), and 3 = almost always (five to seven days per week). Total scores range from 0 to 54, with higher scores indicating greater severity of depressive symptoms.

The results from Lee et al. (2000) demonstrated that the TDS had excellent reliability and validity. The Cronbach's alpha coefficient was 0.90, and the area under the receiver operating characteristic (ROC) curve was 0.92. The TDS also showed good concurrent validity, with a sensitivity of 0.89 and specificity of 0.92 at a cutoff score of 19.

In the present study, the TDS demonstrated excellent internal consistency, with a Cronbach's alpha of .94.

(5) Anxiety:

Anxiety was assessed using the State subscale of the State–Trait Anxiety Inventory (STAI-S; Spielberger, Gorsuch, & Lushene, 1970), a widely used and psychometrically validated instrument. The STAI-S consists of 20 items that assess anxiety-related feelings, thoughts, and behaviors at the time of assessment. Each item is rated on a 4-point Likert scale ranging from 1 (“not at all”) to 4 (“very much so”). Items 1, 2, 5, 8, 10, 11, 15, 16, 19, and 20 are reverse-scored. Total scores range from 20 to 80, with higher scores indicating greater levels of state anxiety. Scores between 20–39 indicate mild anxiety, 40–59 moderate anxiety, and 60–80 severe anxiety.

In the present study, the validated Chinese version of the STAI-S, adapted by Wang and Chung (2016), was used. Their study confirmed the multidimensional factorial structure of the Chinese version and demonstrated good psychometric properties, including adequate convergent and discriminant validity. In the present sample, the STAI-S showed excellent internal consistency (Cronbach's $\alpha = .95$).

(6) Job Stress:

Perceived job stress was measured using the **14-item Work Pressure Inventory** developed by Huang et al. (2017), which has demonstrated good internal consistency. The scale comprises three dimensions: low self-development, workload, and job characteristics. Each item is rated on a 5-point Likert scale ranging from 1 ("strongly disagree") to 5 ("strongly agree"), with total scores ranging from 14 to 70. Higher scores indicate greater perceived occupational stress. In the original validation study, the Cronbach's α coefficients for the three subscales were 0.81, 0.73, and 0.77, respectively. In the present study, the Work Pressure Inventory showed good overall internal consistency (Cronbach's $\alpha = .84$).

(7) Occupational burnout:

Occupational burnout was assessed using the **Chinese version of the Copenhagen Burnout Inventory** (CBI; Yeh et al., 2008), which has demonstrated good psychometric properties in Taiwanese populations. The scale consists of four subscales: personal burnout, work-related burnout, client-related burnout, and overcommitment to work. Each item is rated on a five-point frequency scale: "always" (100), "often" (75), "sometimes" (50), "rarely" (25), and "never" (0). Subscale scores are calculated as the average of the items within each domain, ranging from 0 to 100, with higher scores indicating more severe occupational burnout. **The original validation study reported Cronbach's α values above 0.84 across all subscales (Yeh et al., 2008). In the present study, the scale demonstrated excellent internal consistency (Cronbach's $\alpha = .95$).**

(8) Resilience:

Resilience was measured using the 10-item Resilience Scale developed and validated by Hsiao et al. (2019) for use among hospital staff in Taiwan. The scale assesses individuals' psychological capacity to adapt to and recover from stress and adversity. Each item is rated on a 5-point Likert scale ranging from 1 ("strongly disagree") to 5 ("strongly

agree”), with total scores ranging from 10 to 50. Higher scores indicate greater levels of psychological resilience.

The original validation study demonstrated strong psychometric properties, including good model fit from confirmatory factor analysis ($GFI = 0.973$) and excellent internal consistency (Cronbach’s $\alpha = .91$). The authors also found that resilience levels varied by gender and years of service, highlighting the tool’s sensitivity in occupational contexts.

In the present study, the scale showed excellent internal consistency (Cronbach’s $\alpha = .92$).

All instruments used in this study were authorized by the original developers and have been psychometrically validated in previous research. In the present study, all scales demonstrated good to excellent internal consistency, with Cronbach’s α values ranging from .84 to .95.

Statistical Analysis

All statistical analyses were conducted using IBM SPSS Statistics version 30.0. Continuous variables were summarized as mean \pm standard deviation (SD), and categorical variables as n (%). Baseline group comparability was assessed using independent-samples t tests (continuous variables) and χ^2 tests (categorical variables). Variables that differed significantly at baseline ($p < .05$) were considered potential confounders; because age differed significantly between groups, it was included as a covariate in all longitudinal models.

Within-group changes from baseline (weeks 0–8) were examined using paired t tests. Between-group comparisons at each follow-up time point were performed using independent-samples t tests. For significant between-group differences, effect sizes were calculated using Cohen’s d with 95% confidence intervals (CI), where 0.2, 0.5, and 0.8 indicated small, medium, and large effects, respectively.

To assess the longitudinal effects of the intervention, generalized estimating equations (GEE) were applied with a normal distribution, identity link, and an exchangeable correlation structure. The model included group (intervention vs. control), week (categorical: 0–8), the group \times week interaction, and age as a covariate. Robust (sandwich) standard errors were used. Regression coefficients (B), standard errors, Wald χ^2 statistics, 95% CIs, and p values for group \times week contrasts are reported. GEE was chosen over repeated-measures ANOVA or generalized linear mixed models because it provides population-averaged estimates, is robust to correlation misspecification, accommodates missing data under MAR/MCAR assumptions, and does not require sphericity. All tests were two-tailed with $\alpha = .05$.

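### Age became a covariate through a baseline significance test between randomised arms; this hardly touches the GEE contrasts, but the weekly t tests and their Cohen's d have no adjustment at all

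*Combined protocol and SAP*

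**What the plan says.** Under Methods, 160 nurses were allocated 1:1: "They were randomly assigned via computer to the intervention group" or to control, 80 in each.

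Under Statistical Analysis, "Baseline group comparability was assessed using independent-samples t tests" for continuous variables, with chi-square tests for categorical ones. The selection rule and its outcome follow in one sentence: variables that differed at p < .05 "were considered potential confounders; because age differed significantly between groups, it was included as a covariate in all longitudinal models". The GEE then contains group, week (a factor with levels 0 to 8), and their "interaction, and age as a covariate". It uses an exchangeable working correlation and robust standard errors, and the group × week contrasts are what is reported.

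The same section also compares the arms at each follow-up week by independent-samples t tests and attaches Cohen's d with a 95% CI to the significant ones. No covariate is mentioned for these tests.

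Under Instruments, the Demographic Data item lists 21 variables, among them "experience with COVID-19 patient care, employment start date, external hospital experience, total years in nursing", as well as medication use, sleep quality and sleep disorders. The plan does not say which of these were tested. It gives no covariate list that is independent of the tests and no reason for any covariate based on its relation to outcome.

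**The concern.** Under computer randomisation, a baseline difference between arms is a chance difference. Its p-value measures how unusual the draw was, not whether the variable predicts distress or depression. A p < .05 filter can therefore admit a variable that has no bearing on outcome and leave out a useful predictor whose imbalance falls just short of the cut-off. The choice is also made by looking at data by arm, so the age-adjusted model cannot be presented as fixed in advance.

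What is at stake differs between the two planned analyses. The selected covariate goes only into the longitudinal models. The weekly t tests receive nothing, not even the variable that the plan itself calls a potential confounder. The question is where adjustment would change a reported result.

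**Working it through.** The documents give no sample-size, power, effect-size or correlation figure, so there is nothing of the plan's own to reproduce.

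**Inputs**
- From the documents: 80 per arm; two-sided alpha 0.05; 21 listed baseline items, about 20 distinct because date of birth duplicates age; 7 baseline scales; GEE with week 0 in the response and age as a main effect; unadjusted weekly t tests.
- Assumed: covariate–outcome correlation r = 0.1 to 0.5; baseline–follow-up correlation ρ = 0.3 to 0.8; true effect 0.4 SD.

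**1. Flags expected by chance.** Expected number = k × 0.05.
- k = 20: 1.0 flag; P(at least one) = 1 − 0.95^20 = 0.64.
- k = 27 (adding the 7 scales): 1.35 flags; 1 − 0.95^27 = 0.75.

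The probabilities assume independent tests. Age, employment start date and years in nursing are evidently related, which lowers the probabilities but not the expected counts. One flagged variable is what chance alone would give.

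**2. Imbalance needed for a flag.** 1.96 × √(2/80) = 1.96 × 0.158 = 0.31 SD.

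**3. Effect on the GEE contrasts.** Write E(Y at week w) = b0 + b1·group + c_w + d_w·group + a·age, with c_0 = d_0 = 0. Then E(Y at week w − Y at week 0) = c_w + d_w·group. The age term drops out, as would any time-constant main effect. In a simulated data set (80 per arm, weeks 0–8, exchangeable GEE, robust SE, age imbalanced), the week-2 contrast was:

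| Model | Complete data | 15% of follow-up records deleted at random |
|---|---|---|
| no covariate | −0.285321 (SE 0.14096) | −0.458 (SE 0.138) |
| + age | −0.285321 (SE 0.14096) | −0.456 (SE 0.138) |
| + age + a stronger predictor | −0.285321 (SE 0.14096) | −0.454 (SE 0.138) |

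Only the group main effect moved (0.066 to 0.027 with age, complete data). In this parametrisation that is the week-0 difference, not a treatment effect.

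**4. Effect on the weekly t tests.** Nothing cancels here. Shift = r × imbalance.
- Imbalance 0.30 SD (p = .06: 1.88 × 0.158 = 0.30) and r = 0.5: 0.5 × 0.30 = 0.15 SD.
- Age was flagged, so if it was compared by t test on all 160 nurses its imbalance is at least about 0.31 SD. The shift in an unadjusted weekly difference is then at least 0.03 SD at r = 0.1, 0.09 at r = 0.3 and 0.16 at r = 0.5. The documents do not give r for age.
- Type I error given the p = .06 imbalance, r = 0.5: the test statistic has mean 0.5 × 1.88 = 0.94 and SD √(1 − 0.25) = 0.866, so P(|statistic| > 1.96) = 0.12. In a simulation, the contrast of change from week 0 under the same imbalance had 5.0%.

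**5. Gain from adjusting the weekly comparison for the week-0 score.** Power = Φ(0.4 / (s × √(2/80)) − 1.96), with s = 1 unadjusted and s = √(1 − ρ²) adjusted. At ρ = 0.5:
- unadjusted: 0.4 / 0.158 − 1.96 = 0.57, power 0.716;
- adjusted: 0.4 / (0.866 × 0.158) − 1.96 = 0.96, power 0.832.

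| ρ | 0.3 | 0.4 | 0.5 | 0.6 | 0.7 | 0.8 |
|---|---|---|---|---|---|---|
| unadjusted t test | 0.716 | 0.716 | 0.716 | 0.716 | 0.716 | 0.716 |
| adjusted for week-0 score | 0.756 | 0.788 | 0.832 | 0.885 | 0.943 | 0.988 |

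**The case against.** The strongest reply is that the rule does no harm where it acts. It feeds only the GEE, whose reported contrasts are differences in change from week 0, and step 3 shows that the choice of a main-effect covariate leaves them unchanged with complete data and nearly so with 15% missing. The weekly t tests are unadjusted whatever the baseline tests show, so deleting the rule would not by itself alter them. They are also valid on average over randomisations; the 12% applies only given an imbalance of that size. All of this stands, and it limits the point.

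A reader might infer that stronger predictors than age were collected and left out. The documents do not show this. They give no predictor strengths, and the only link they report is under Resilience, where gender and years of service were related to resilience scores. Sleep quality, sleep disorder and medication use are plausible predictors, no more. Nor is the most plausible strong predictor, each outcome's own baseline score, ignored in the GEE, since it enters as the week-0 response.

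A reader might also infer that choosing covariates by p-value distorts power or type I error in the longitudinal analysis. That would follow if a single-week comparison were adjusted for whichever covariates were flagged, but the plan contains no such analysis.

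Two things survive the reply. The stated reason for adjusting for age is not a prognostic one and arose from data by arm. And the weekly comparisons forgo precision that data already collected could supply.

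**Conclusion.** The point holds in a limited form. Covariate selection by baseline significance test is unsound between randomised arms, and the document states it as the only reason for including age. Its numerical consequence for the reported GEE contrasts is close to nil. That rests on age entering as a main effect only, on week 0 being in the response, and on data that are complete or nearly so.

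The consequence that matters lies in the weekly t tests and their Cohen's d: a shift of about 0.15 SD for a covariate with r = 0.5 and a 0.30 SD imbalance, and power of about 72% where adjustment for the week-0 score would give 83% (ρ = 0.5, effect 0.4 SD; 76% to 99% for ρ from 0.3 to 0.8). The values of r, ρ and the effect are assumptions. This is a worthwhile, inexpensive improvement; it does not show that the longitudinal results are wrong.

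**What to change.** 1. Delete the p < .05 rule and keep the baseline table descriptive, with standardised differences if wanted.
2. Replace the weekly t tests with adjusted comparisons, and derive the reported effect sizes from them. Possible wording:

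> At each of weeks 1 to 8 the arms are compared by linear regression on group, adjusted for the week-0 score of the same outcome, age and self-rated sleep quality. The set is the same for all outcomes and was chosen without reference to differences between groups. Baseline characteristics are described without significance tests.

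   Total years in nursing could stand in place of age. A GEE for weeks 1 to 8 with the week-0 score and its interaction with week would give the same comparisons in one model; in the simulated complete data set it cut the week-2 standard error from 0.141 to 0.124.
3. State that age was adjusted for after its imbalance had been seen, and show the between-group results with and without it. The GEE contrasts should barely differ; the weekly comparisons may.
4. Data collection ended in September 2024, so a list drawn up now should be reported as a revision, with its prognostic reasons. If data guide the choice, use associations with outcome in both arms pooled.

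The cost is a change of wording, one re-run on data already held, a few degrees of freedom out of 160, and the loss of the baseline p-value column.

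### The age term has little or no effect on the reported group × week coefficients, and the weekly t tests and Cohen's d use neither age nor the week 0 score

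*Combined protocol and SAP*

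**What the plan says.** All of the analysis text is in the Statistical Analysis section.

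- **Choice of covariate.** Baseline variables that differ at p < .05 are treated as potential confounders. Age is the one named: "because age differed significantly between groups, it was included as a covariate in all longitudinal models".
- **Longitudinal model.** A GEE with normal distribution, identity link, exchangeable correlation and robust standard errors. Its terms are group, week as a category from 0 to 8, and the group × week "interaction, and age as a covariate". No age × week term is listed.
- **What is reported from it.** B, standard error, Wald statistic, CI and p value; the sentence ends by saying that group × "week contrasts are reported".
- **Weekly comparisons.** "Between-group comparisons at each follow-up time point were performed using independent-samples t tests". Next comes "For significant between-group differences, effect sizes were calculated using Cohen" (the sentence goes on to d with a 95% CI and benchmarks of 0.2, 0.5 and 0.8). No covariate is named for either.
- **Missing data.** GEE is preferred partly because it "accommodates missing data under MAR/MCAR assumptions". No amount is given, and Interventions says that "all participants in both groups were followed for 8 weeks and completed weekly questionnaires".
- **Timing.** Methods states: "The study was conducted from June 13, 2024, to September 22, 2024". Data collection is therefore over.

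**The concern.** Having found an age imbalance, the plan adds age where it does little. Someone reading that age is in every longitudinal model may suppose that the reported group × week coefficients were corrected for the imbalance. With complete data they are the same numbers as without age.

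The weekly t tests and Cohen's d compare raw scores rather than changes. They are the results that an age effect on level could reach, and no adjustment is described for them. They also ignore the week 0 score, which is already collected and would usually make the comparison more precise. At stake are how the weekly effect sizes should be read given the imbalance that occurred, and some lost precision.

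**Working it through.** The plan states no figure on this point, so there is none to reproduce.

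**Inputs from the documents.** 80 per arm; weeks 0 to 8; two-sided α = .05; the GEE terms above; age different at p < .05.

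**Assumed inputs (not in the documents).** Age imbalance d, age–outcome correlation, week 0–8 correlation r, and missingness.

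**1. Why age drops out of the coefficients.** The model mean for person i in arm g at week w is μ(g,w) + γ·age(i). The change from week 0 is μ(g,w) − μ(g,0), and γ·age(i) cancels. With complete data and exchangeable correlation, B for week w is the raw difference between arms in mean change, whether or not age is included.

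Check on one simulated complete dataset (80/80, 9 weeks, no true effect, age related to both level and change):

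- Week 8 coefficient: −0.8563 without age, −0.8563 with age; raw difference in mean change −0.8563.
- Largest movement across the eight coefficients: about 3e-15; in their SEs, about 6e-15.
- Group main effect (the week 0 difference): −0.093 without age, 0.443 with age.
- With age × week added, the week 8 coefficient becomes −0.257 (SE 0.703, against 0.691).

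The cancellation is algebraic and does not depend on the assumed values.

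**2. The other reading of the contrasts.** If the term means the model-based group difference at each week (group main effect plus B), age does act. In the same example every weekly difference shifts by 0.443 − (−0.093) = 0.536. Such differences are adjusted for a constant age effect. The sentence pairs the contrasts with B but does not say which is meant.

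**3. If weeks are missing.** I simulated 200 datasets per setting, with assumed imbalance 0.4 SD, age–level correlation 0.3 and within-person correlation 0.3 or 0.6. The largest of the eight shifts caused by the age term was:

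| Missingness (assumed) | Median, in SEs | Maximum, in SEs |
|---|---|---|
| 15% completely at random | 0.02–0.05 | 0.06–0.14 |
| Dropout unrelated to age, 65% retained | 0.04–0.08 | 0.17–0.30 |
| Age-related dropout, same in both arms, 62% retained | 0.05–0.08 | 0.27–0.36 |
| Strong age-related dropout, opposite by arm | 0.39–0.64 | 0.67–0.98 |

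Only the last, extreme setting makes the age term matter much. The documents give no basis for any of these rates.

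**4. Smallest imbalance consistent with p < .05.** t(0.975, 158) × √(2/80) = 1.975 × 0.158 = 0.312 SD. As an assumed upper value I take 0.5 SD (t = 0.5/0.158 = 3.16).

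**5. Possible bias.** Approximately imbalance × correlation.

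- Age correlated 0.1–0.3 with level only: bias in Cohen's d from 0.312 × 0.1 = 0.03 to 0.5 × 0.3 = 0.15. Given that imbalance, the t test's false-positive rate was 5.3%–14.2% in simulation. The group × week contrast was unbiased.
- Age correlated 0.1–0.3 with change: the group × week contrast is biased by the same 0.03 to 0.15, now in SDs of change (5.3%–14.3%). Adding age × week, or using the weeks 1–8 model, brings this to 0.00.

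**6. Precision.** SE ratios:

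- age × week against the current contrast: √(1 + d²/4) = 1.012 (d = 0.312) to 1.031 (d = 0.5);
- weeks 1–8 model against the t test: √[(1 − r²)(1 + d²/4)];
- weeks 1–8 model against the current contrast: the previous ratio divided by √[2(1 − r)].

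| r | vs t test | vs current contrast |
|---|---|---|
| 0.4 | 0.93–0.94 | 0.85–0.86 |
| 0.6 | 0.81–0.82 | 0.91–0.92 |
| 0.8 | 0.61–0.62 | 0.96–0.98 |

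Break-even with the t test: r² = (d²/4)/(1 + d²/4), so r = 0.15 at d = 0.312 and 0.24 at d = 0.5.

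**The case against.** The best defence is that nothing here is shown to be harmed. The GEE is the analysis assigned to the longitudinal effect, and differencing from week 0 already protects its contrasts from a constant age effect. Allocation was random, so unadjusted t tests are valid and the plan does not present them as adjusted. Instruments lists about 21 demographic items; if all were tested, 21 × 0.05 ≈ 1 would differ at p < .05 by chance. Every magnitude above rests on assumed inputs. The nearest support for a link with age is the remark under Resilience that scores varied by years of service in an external validation study. It covers one outcome, gives no size, concerns level rather than change, and needs a further assumption to reach age.

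All of that stands, and it rules out several stronger readings that a reader might infer:

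- *That the GEE results are biased by age.* This would need a relation between age and change, and none is documented.
- *That the plan wrongly calls its coefficients age-adjusted.* It says only that age was included, which is accurate.
- *That substantial missing data are expected.* The plan only lists tolerance of missing data among its reasons for choosing GEE, and Interventions says that everyone completed the weekly questionnaires.
- *That the t tests are invalid.* They are not.

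The defence does not answer the narrower point. The plan itself names age as a potential confounder, yet its only stated effect size is described without age, and the coefficients from the model that contains age do not move with complete data.

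**Conclusion.** The point holds in a limited form and is worth fixing. That the age main effect leaves the group × week coefficients unchanged is exact for complete data under the stated GEE, if the contrasts are the interaction coefficients. That the t tests use no covariate follows from their description. That Cohen's d is unadjusted is inferred from its placement directly after them, since no formula is given.

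The consequence for bias is probably small and undetermined. The upper figure of 0.15 SD and the false-positive rates near 14% need both the largest assumed imbalance and the largest assumed correlation, and they are conditional on that imbalance. The case for change therefore rests mainly on two things: placing the adjustment where it has an effect, and using week 0 scores already in hand, which gains precision unless the week 0–8 correlation is low.

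**What to change.** 1. As the main weekly between-group estimates, report model-based group differences with CIs at each of weeks 1–8, from a model of the post-baseline scores with baseline score × week, age × week and group × week. Base the effect size on these differences.
2. Label this analysis post hoc, because data collection has ended. Keep the existing t tests and GEE as supporting results so that both sets can be seen.
3. State whether the group × week contrasts are interaction coefficients or weekly group differences. If they are interaction coefficients, note that the age main effect does not alter them with complete data, and add age × week as a sensitivity analysis.
4. State that the supporting t tests and Cohen's d are unadjusted, if that is so.

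The cost is a rerun on existing data. Mean parameters per outcome go from 19 (1 + 1 + 8 + 8 + 1) to 27 with age × week (19 + 8), or 32 for the weeks 1–8 model (8 weeks × 4 terms), with 160 participants. If age is unrelated to change, age × week enlarges the SE of the contrast by about 1%–3%. The weeks 1–8 model loses to the t test only below a week 0–8 correlation of about 0.15–0.24. Both figures assume an age imbalance of 0.31–0.5 SD.
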